10.4.1 Salmeterol/Fluticasone Run-in

A separate subject listing will be provided detailing the administration of salmeterol and fluticasone during the 30day runin period prior to randomization, for the SAS. The listing will display for each subject whether the 30day runin period was started, completed without interruption, and whether the dose was tapered and discontinued as per protocol, for salmeterol and fluticasone use during the runin period, as applicable. Reason/s for not receiving salmeterol and/or fluticasone per protocol specifications will also be presented, as applicable.

10.5 Treatment Exposure

Based upon the PK of the study drug (halflife of 18.0 to 27.0 days) and dosage administered, each dose will count as 28 days of exposure to study drug. Therefore, days of exposure to study drug will be calculated as:

$$(last\ study\ drug\ dose\ date - first\ study\ drug\ dose\ date) + 28$$

A subject listing of treatment exposure will be presented, using the SAS, including the date and time of each study drug administration, reason for a dose not administered, location of each injection for each study drug administration, confirmation whether the injections were administered 4-10 cm from the umbilicus (with reason if not), and whether the complete dose was administered (with reason if not). The study drug exposure (days) will also be included in the listing.

Exposure to study drug (days) will be summarized by treatment group and overall using descriptive statistics, for the SAS. The number and percentage of subjects receiving 3, 2, 1, and 0 doses of study drug, respectively, will also be presented.

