### 9.4 Treatments Administered

Eligible subjects will receive 600 mg AVTX-002 or placebo SC on Visit 2 (Day 0), Visit 5 (Day 28), and Visit 7 (Day 56).

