## 10.1 Study Duration

AVTX-002 and placebo treatment will be administered at Visit 2 (Day 0), Visit 5 (Day 28), and Visit 7 (Day 56). **A subject may not be dosed after Day 56.** The duration of the treatment period is considered 84 days, with each dose of study drug considered to be 28 days of treatment. The overall study period is approximately 135 days, including Screening and the 30-day, stabledose, run-in period.

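### The SAP's exposure formula uses only the first and last dose dates, so it does not implement the stated rule of 28 days per dose; the gap is 25 to 28 days if the middle dose alone is missed.

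*SAP*

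**What the plan says.** SAP 10.5 (Treatment Exposure) cites the drug's half-life and the dose given, and sets the rule that "each dose will count as 28 days of exposure to study drug". It then presents a formula as following from that rule: last dose date minus first dose date, plus 28.

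Protocol 10.1 (Study Duration) holds the same rule: "The duration of the treatment period is considered 84 days, with each dose of study drug considered to be 28 days of treatment". Protocol 9.4 schedules doses on Days 0, 28 and 56, and Protocol 10.1 adds that "A subject may not be dosed after Day 56". In Protocol Table 1, Visit 5 has a window of 3 days either side and Visit 7 may be up to 3 days early.

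For the safety set, SAP 10.5 also plans a listing of every administration, including the "reason for a dose not administered", and a dose-count summary: "The number and percentage of subjects receiving 3, 2, 1, and 0 doses of study drug, respectively, will also be presented".

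**The concern.** The rule counts doses. The formula measures elapsed time from first to last dose and adds one interval. They are equivalent only if consecutive doses are exactly 28 days apart with none left out, and nothing in SAP 10.5 limits the formula to that case.

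The clearest failure is a subject who receives the first and third doses but not the second. The formula gives that subject the same exposure as one who received all three, although Protocol 8.7 and 12.3.1.1 define completion of therapy as three doses. At stake is the accuracy of the exposure summary and listing against the definition both documents state.

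**Working it through.** **Inputs.**
- Rule: 28 days per dose (SAP 10.5, Protocol 10.1).
- Formula: last dose date − first dose date + 28 (SAP 10.5).
- Scheduled dose days: 0, 28, 56 (Protocol 9.4).
- Windows: Visit 5 on Days 25 to 31, Visit 7 on Days 53 to 56 (Protocol Table 1).

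Days use protocol numbering. SAP Section 8 relabels Day 0 as Day 1, which moves both dates equally and leaves the difference unchanged.

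**The plan's own figure.** Three doses on schedule: formula 56 − 0 + 28 = 84; rule 3 × 28 = 84. Both reproduce the 84-day treatment period in Protocol 10.1.

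**Other dosing patterns.** The last column counts the distinct days covered by a 28-day window starting at each dose.

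| Dose days | Formula | 28 × doses | Formula − rule | Distinct days covered |
|---|---|---|---|---|
| 0, 28, 56 | 56 + 28 = 84 | 84 | 0 | 84 |
| 0, 28 (third not given) | 28 + 28 = 56 | 56 | 0 | 56 |
| 0 only | 0 + 28 = 28 | 28 | 0 | 28 |
| 0, 28, 53 | 53 + 28 = 81 | 84 | −3 | 81 |
| 0, 25 | 25 + 28 = 53 | 56 | −3 | 53 |
| 0, 31 | 31 + 28 = 59 | 56 | +3 | 56 |
| 0, 31, 56 | 56 + 28 = 84 | 84 | 0 | 81 |
| 0, 56 (middle missed) | 56 + 28 = 84 | 56 | +28 | 56 |
| 0, 53 (middle missed) | 53 + 28 = 81 | 56 | +25 | 56 |

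**Reading the table.**
- On-schedule dosing, complete or stopped early: no difference.
- Doses moved within their windows: up to 3 days in either direction. Three-dose subjects can be affected, as Days 0, 28 and 53 show.
- Middle dose missed: 25 to 28 days too many against the rule, that is 25/56 = 45% to 28/56 = 50%.

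**Effect on a group mean.** The documents do not say how many subjects might miss only the middle dose. Taking the planned 40 per arm as the denominator, each such subject dosed on Days 0 and 56 raises that arm's mean exposure by 28/40 = 0.7 days.

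**Where the variable is used.** Only in the SAP 10.5 listing and descriptive summary. The treatment-emergent definition (SAP Section 8 and 10.7.1) and the repeat of the primary analysis through 28 days after the final dose (SAP 10.6.3) use the last dose date. The annual event rate (SAP 6.2.1) uses duration of study participation.

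**The case against.** The best defence is that first dose to last dose plus one interval is a sensible measure of exposure span. At the SAP's half-life of 18.0 to 27.0 days, simple first-order decay leaves 0.5^(28/18) = 34% to 0.5^(28/27) = 49% of the drug after 28 days, so a subject with a gap is not drug-free. That would justify a span definition if the SAP stated one. It states a per-dose count and offers the formula as its consequence, so one of the two sentences has to change.

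Three further points limit the concern, and they stand.

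- A reader might infer from the dose-not-administered item and the dose-count summary that the SAP expects skipped doses. Both fit early stopping equally well, and early stopping is the route the protocol describes (Protocol 8.7, 9.11.4, 10.2.2.1). The row for 0 doses is generic: the safety set requires at least one dose, so that row is empty by definition. Protocol Section 10 asks for missed visits to be rescheduled as soon as possible, so a late second dose is at least as plausible as an omitted one. It also refers dosing decisions to the medical monitor when a visit cannot be held in clinic, and nothing bars a third dose after a missed second. The pattern is therefore possible, but not shown to be expected.
- A reader might infer that the days summary would contradict the dose-count summary. It would not. One counts doses and the other days, and the dose count, the listing of each administration and the per-subject figures in SAP 10.6.1 would all reveal a gap.
- A reader might infer that safety conclusions are distorted. As shown above, no test, window or rate uses exposure days.

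**Conclusion.** The inconsistency is real and minor. SAP 10.5 states one definition of exposure and computes another. They coincide for on-schedule dosing and for on-schedule dosing that stops early, differ by up to 3 days through permitted visit windows, and differ by 25 to 28 days when only the middle dose is missed. It would be wrong to say that subjects with all three doses are never affected, because a Visit 7 dose given on Day 53 gives 81 days against 84.

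This conclusion takes the 28-days-per-dose sentence as the intended definition, since both documents state it. If the sponsor means elapsed span, the formula stands and the rule sentence is what is wrong. How often a lone middle dose would be missed cannot be judged from the documents.

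**What to change.** Replace the formula in SAP 10.5 with exposure (days) = 28 × number of doses received. This matches the stated rule for every pattern in the table and gives 84 days for three doses, as in Protocol 10.1.

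If the sponsor prefers distinct days covered, define exposure as the union of the 28-day windows after each dose and reword the rule sentence to say so. Capping each interval at 28 days and adding 28 for the last dose gives the same result. Neither form should be adopted under the present wording: doses on Days 0, 31 and 56 would give 28 + 25 + 28 = 81, where the rule and the current formula both give 84.

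The cost is one line in the SAP and one in the derivation program. No new data are needed, because every dose date is already collected and listed.

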10.6 Efficacy

The following subject listings will be provided, using the FAS (observed as well as change from baseline values will be included as applicable):

- Occurrence of asthma related events – based on programmatic derivations from raw data (including the specification that constitutes the asthma related event – see [Section 6.2.1](#), date of first administration of study drug, first date of asthma related event/date of last subject visit, the applicable baseline definition – see [Section 9.2](#), time to first asthma related event/time to censoring in days)
- Individual daily recordings for peak flow measurements and number of SABA reliever puffs for subjects with an asthma related event; record/s where criteria for an asthma related event were met, will be flagged in this listing
- Occurrence of asthma related events – based on Investigator assessment (including the specification that constitutes the asthma related event – see [Section 6.2.1](#), date of first administration of study drug, first date of asthma related event/date of last subject visit)
- Discordance between programmatic derivation from raw data and Investigator assessment in occurrence of asthma related events

- FEV₁ (FEV₁ [L]) and FeNO (nitric oxide level [ppb]) results
- ACQ results (results for each individual item as well as the overall score – see [Section 6.2.4](#))
- AQLQ(S)+12 results (results for each individual item as well as the domain and overall scores – see [Section 6.2.5](#))
- ASD results (see [Section 6.2.6](#)) – this will include the following:
 - mean symptom scores for each symptom separately, as well as mean ASD scores, for each 1-week period
 - number of SABA reliever puffs (mean daily puffs/inhalations over each 1-week period)
 - peak flow measurements (mean measurement over each 1-week period)

Note: Only the weekly mean data are presented by subject in these subject listings; all individual daily recordings are however available in the submission datasets.

- EQ-5D-5L results (results for each of the 5 dimensions as well as for the EQ VAS – see [Section 6.2.7](#))
- PGI-C/S and CGI-I/S results (results for each question – see [Section 6.2.8](#) and [Section 6.2.9](#))

10.6.1 Primary Endpoint Analysis

The primary endpoint analysis is performed using the assessments for the occurrence of asthma related events based on programmatic derivations from raw data.

The proportion of subjects who experience any asthma related event will be summarized by treatment group, also including the proportion of subjects who experience each of the 5 separate criteria for an asthma related event (as identified in [Section 6.2.1](#)). A subject who experienced multiple asthma related events will be counted once in each of the applicable criteria categories and once for having an asthma related event.

Summary statistics showing the number and percentage of subjects with and without asthma related events in each treatment group will be provided via a 2x2 table. Comparison of the proportions of subjects who had an asthma related event will be via a Wald Z-test (including and without continuity correction). The test statistic, its associated p-value and a 95% confidence interval for the treatment difference will also be provided.

The summary table and associated statistical analysis of the occurrence of asthma related events will be repeated for results obtained using each of the 4 baseline values for mean daily number of SABA puffs/inhalations and mean peak flow rate calculated according to Definitions 1 to 4 in [Section 9.2](#), for all subjects in the FAS. In addition, the results for occurrence of asthma related events using the baseline values for mean daily number of SABA puffs/inhalations and mean peak flow rate calculated according to Definition 1 in [Section 9.2](#), for subjects in the Per Protocol Analysis Set, will also be presented.

Figures (one per subject) will display the % change from baseline in peak flow rate and change from baseline in daily number of SABA puffs/inhalations over time. Baseline values calculated according to Definition 1 in [Section 9.2](#) will apply. Occurrence of the following will also be

indicated on the figure for each subject: administration of each dose of study drug, reduction of fluticasone dose, discontinuation of salmeterol and fluticasone, end of study participation. As part of the figure, information on subject disposition (whether the subject completed the study or reason for early discontinuation from the study) and whether any criteria for occurrence of an asthma related event were met, will also be displayed.

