6.1.1 Justification of Sample Size

The sample size in this study will be approximately 80 subjects, ie, 40 subjects per treatment arm, randomized in a 1:1 ratio.

The sample size estimate was based on the estimated proportions of subjects in the 2 treatment groups expected to have an asthma related event as defined by the primary endpoint. In a study of similar design with another asthma controller therapy, rates of 6% in the active group and 44% in the placebo group were observed [3]. If these estimates were used as is, then a study with 40 subjects per group would have over 95% power. Considering likely variations from the cited study, estimates of sample were assessed assuming a Type I error of 5% and the proportion of subjects with an asthma related event ranging from 30% to 50% in the placebo group and 5% to 8% in the active group. In the 20 such scenarios examined, only in the cases in which the difference between treatments gets below 23% does the power fall slightly below 80%. In the vast majority of cases examined the power is greater than 90%.

The overall event rate may be assessed in a blinded fashion when an adequate amount of subject followup has occurred. If this event rate is found to be much lower than assumed, a sample size reestimation may be performed.

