9.2 Baseline and Related Changes Definition

In general and unless otherwise specified, baseline is defined as the last available assessment prior to the first dose of the study drug.

CFB is calculated as: $CFB = observed\ value - baseline\ value$

CFB% is calculated as: $CFB\% = \left(CFB / \text{baseline value} \right) \times 100$ (if the baseline value is 0, CFB% cannot be calculated)

Where unscheduled/repeat assessments are relevant and exist for any subject at a particular visit they will also be considered in the baseline definitions, provided they remain prior to the first dose of study drug.

Visit 1a (Day 7 [2 days]) with diary activation was added to the protocol Schedule of Assessments in Protocol Version 4.0 (Amendment 3), 05 May 2022. Therefore, subjects enrolled prior to this amendment did not have a diary activated until the day of randomization (ie, they will not have diary entries during the 7 days preceding Visit 2). A baseline value cannot be calculated for subjects with no diary entries before the day of randomization. To include such subjects in analyses, additional definitions of baseline have been included in which Day 1 entries or Day 1 through Day 7 entries may be used for calculation of baseline when a subject does not have sufficient diary entries prior to Day 1. This approach has been taken given that all subjects have received a 30day regimen of stable asthma medications leading up to Day 1 which will be maintained until Day 14 per protocol; therefore, a Day 1 (or Day 1 through Day 7) diary entry is a reasonable representation of their baseline. The baseline definitions are detailed below for each of the following subject diary assessments:

Asthma Symptom Diary Assessment	Baseline Definition

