	
 Subjects whose diary was activated no later than Day -1, will have their baseline value calculated as: $\frac{\text{sum of daily sums from Day -7 through Day -1}}{\text{number of days the diary was available from Day -7 through Day -1}}$ Subjects for whom their diary was not activated by Day -1 but for whom the diary was activated on Day 1 and ≥ 1 Day 1 entry is available, will have their baseline value calculated as: $\frac{\text{sum of entries on Day 1}}{\text{number of days the diary was available from Day 1 through Day 1}}$ Subjects for whom their diary was not activated by Day 1, will have a null baseline.
	Definition 2:
	
 Subjects whose diary was activated no later than Day -1, will have their baseline value calculated as defined in Definition 1 above. Subjects for whom their diary was not activated by Day -1 but for whom the diary was activated for ≥ 1 day between Day 1 and Day 7, will have their baseline value calculated as: $\frac{\text{sum of daily sums from Day 1 through Day 7}}{\text{number of days the diary was available from Day 1 through Day 7}}$ Subjects for whom their diary was not activated by Day 7, will have a null baseline.
	Definition 3:
	
 Subjects whose diary was activated no later than Day -1, will have their baseline value calculated as defined in Definition 1 above. Subjects for whom their diary was not activated by Day -1, will have a null baseline.
	Definition 4:
	
 Subjects whose diary was activated no later than Day -4, will have their baseline value calculated as defined in Definition 1 above. Subjects for whom their diary was not activated by Day -4, will have a null baseline.
	Note: for the days the diary was available (ie, any day from diary activation through deactivation), all missing entries will be considered 0 for calculation of the baseline value
Mean peak flow rate	Baseline values will be calculated by the following 4 separate definitions. The primary baseline definition (Definition 1) will be used for all output that requires a comparison of peak flow rate to baseline. Definition 2 through 4 will only be used for the primary endpoint summary in the FAS and associated listings (ie, occurrence of an asthma related event; see Section 6.2.1).

Definition 1 (primary baseline definition):

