- Subjects with ≥ 1 of the expected 7 entries from Day -7 through Day -1, will have their baseline value calculated as:

$$\frac{\text{sum of available entries from Day -7 through Day -1}}{\text{number of available entries from Day -7 through Day -1}}$$

- Subjects with no entries from Day -7 through Day -1 but for whom the Day 1 entry is available, will have their baseline value calculated as:

$$\text{Day 1 entry}$$

- For subjects with no entries from Day -7 through Day 1, the baseline value will be missing.

Definition 2:

- Subjects with ≥ 1 of the expected 7 entries from Day -7 through Day -1, will have their baseline value calculated as defined in Definition 1 above.
- Subjects with no entries from Day -7 through Day -1 but for whom ≥ 1 entry between Day 1 and Day 7 is available, will have their baseline value calculated as:

$$\frac{\text{sum of available entries from Day 1 through Day 7}}{\text{number of available entries from Day 1 through Day 7}}$$

- For subjects with no entries from Day -7 through Day 7, the baseline value will be missing.

Definition 3:

- Subjects with ≥ 1 of the expected 7 entries from Day -7 through Day -1, will have their baseline value calculated as defined in Definition 1 above.
- For subjects with no entries from Day -7 through Day -1, the baseline value will be missing.

Definition 4:

- Subjects with ≥ 4 of the expected 7 entries from Day -7 through Day -1, will have their baseline value calculated as defined in Definition 1 above.
- For subjects with < 4 entries from Day -7 through Day -1, the baseline value will be missing.

ASD = Asthma Symptom Diary; FAS = Full Analysis Set; SABA = short-acting beta agonist

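### The Definition 3 and 4 repeats of the primary analysis keep subjects with a null SABA or peak-flow baseline in the denominator, where, read literally, they count as without an event unless another criterion is met, so these sensitivity estimates are biased.

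*SAP*

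**What the plan says.** SAP 9.2 explains that the pre-dose diary visit was added only in Amendment 3, so earlier enrollees have no diary data from the week before Visit 2: "A baseline value cannot be calculated for subjects with no diary entries before the day of randomization". Definitions 1 and 2 deal with this by falling back on Day 1, or Day 1 to Day 7, entries. Definitions 3 and 4 have no fallback. Under Definition 3 the SABA baseline is null if the diary was not active by Day -1, and the peak-flow baseline is missing if there are no entries from Day -7 to Day -1. Definition 4 is stricter. For SABA: "Subjects for whom their diary was not activated by Day -4, will have a null baseline". For peak flow: "For subjects with < 4 entries from Day -7 through Day -1, the baseline value will be missing".

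SAP 10.6.1 then repeats the summary table, Wald test and interval under each of the four definitions, "for all subjects in the FAS". The table has two outcome columns, with and without an event. SAP 7.1.3 admits a subject to the FAS on a baseline and a post-baseline value of any efficacy assessment, so a null diary baseline does not remove anyone.

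**The concern.** Two of the five event criteria in SAP 6.2.1 (at least 6 extra SABA puffs, and a peak-flow fall of 30% or more, each on 2 consecutive days) are comparisons with a diary baseline. Where that baseline is null, the criterion cannot be evaluated. The table has no unevaluable category, so the subject lands in the event-free column unless something else puts them in the other. An unknown outcome is then treated as a good one.

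Definitions 3 and 4 drop the fallback baseline, so their natural use is to show whether the Definition 1 result depends on it. If the estimate weakens under Definition 3 or 4, the planned table cannot say whether the fallback baseline mattered or whether unevaluable subjects diluted both arms.

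**Working it through.** **Inputs from the SAP.** Section 6.1.1 gives "rates of 6% in the active group and 44% in the placebo group were observed", and a sample size of "approximately 80 subjects, ie, 40 subjects per treatment arm, randomized in a 1:1 ratio", with a 5% type I error. Sidedness is not stated. I take it as two-sided, in line with 10.6.1, where "a 95% confidence interval for the treatment difference will also be provided".

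**Inputs assumed.** Let f be the share of an arm with both diary baselines null, and s the share of events that meet only a diary criterion. Neither is in the documents. I use f = 10-40% and s = 60-90%, and take null status to be unrelated to event risk.

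**The plan's own figure.** SAP 6.1.1 claims over 95% power at 44% v 6% with 40 per arm. Exact enumeration of the unpooled Wald test gives 99.1% without and 98.2% with continuity correction, so the claim is reproduced.

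**Who stays and how they are classed.**
- They stay in the FAS (7.1.3), and 10.6.1 analyses the FAS.
- The rule in 9.1 that requires both a baseline and a later value covers change-from-baseline summaries, not the event proportion.
- Three criteria need no diary baseline: ICS increase, systemic corticosteroids, and hospitalization or ER visit. Events on these still count.
- The SABA rule depends on diary activation and the peak-flow rule on the number of entries, so a subject can be null for one and evaluable for the other.

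**Dilution with equal null shares.** Observed rate = true rate x (1 - f x s), so the difference is multiplied by the same factor.

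| f | s | factor | placebo | active | difference (points) |
|---|---|---|---|---|---|
| 0 | any | 1.00 | 44.0% | 6.0% | 38.0 |
| 10% | 60% | 0.94 | 41.4% | 5.6% | 35.7 |
| 40% | 90% | 0.64 | 28.2% | 3.8% | 24.3 |

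**Unequal null shares (s = 75%).**
- Null share 0% on placebo and 30% on active: 44.0% v 0.06 x (1 - 0.30 x 0.75) = 4.65%, a difference of 39.4 points, wider than 38.
- Null share 30% on placebo and 10% on active: 34.1% v 5.55%, a difference of 28.6 points.

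Neither arm's rate can rise, but the difference can move either way.

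**Power: retain or exclude (exact, continuity-corrected).** Exclusion keeps the expected rates and reduces n to 40 x (1 - f).

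| Rates | f | retained, n = 40 (s = 90% to 60%) | excluded |
|---|---|---|---|
| 44% v 6% | 10% | 96.7% to 97.3% | 97.1% (n = 36) |
| 44% v 6% | 40% | 83.0% to 91.3% | 86.3% (n = 24) |
| 30% v 8% | 10% | 59.1% to 61.2% | 59.4% (n = 36) |
| 30% v 8% | 40% | 36.4% to 47.3% | 40.4% (n = 24) |

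In each row the exclusion figure lies inside the retention range. The dilution is a problem for the estimate, not for power.

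**The case against.** **The classification is inferred.** No sentence says that a null-baseline subject counts as event-free, and 9.2 says the extra definitions exist so that such subjects can be included, which hints that they would otherwise be left out. This stands in part: intent is uncertain. But the inclusion remark describes the Day 1 and Day 1 to 7 fallbacks in Definitions 1 and 2, and leaving subjects out under Definitions 3 and 4 would contradict the all-FAS wording of 10.6.1. Followed as written, the text puts them in the event-free column by default.

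**Stronger readings that do not hold.** A reader might infer that these subjects are event-free outright. They are not, because three criteria, and sometimes the other diary criterion, remain open to them. A reader might infer that the difference must shrink. That needs similar null shares and similar diary-only shares in the two arms, which randomization makes likely but does not guarantee. A reader might infer a loss of power that exclusion would recover. The power comparison shows otherwise.

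**Retention has merits.** It keeps every FAS subject and every observed steroid or hospital event. Restriction leaves mostly post-Amendment 3 enrollees, so setting Definition 1 in the full FAS against Definition 3 in a subset would compare different people. This stands, and it shapes the fix.

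**Part of the effect would be visible.** The plan already tabulates each criterion separately and lists events with the baseline definition used. That helps a careful reader, but it does not give the number evaluable or an undiluted estimate.

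**Conclusion.** The concern holds for the Definition 3 and 4 sensitivity analyses. As written, they mix a change of baseline with a default to no event for subjects who cannot be assessed on one or both diary criteria. With similar null shares by arm, f of 10-40% and s of 60-90%, a 38-point difference would appear as about 36 to 24 points. Both ranges are assumptions, the lower end needs both extremes together, and the model takes both diary baselines as null at once.

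The Definition 1 result is not what is at issue. Definitions 1 and 2 can also give a null baseline, but only where the fallback entries are absent too, so they are much less exposed. The fault is confined to the interpretability of sensitivity runs, but it should be corrected because it undermines what those runs can show and costs little to mend.

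**What to change.** In SAP 10.6.1, for Definitions 3 and 4:

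1. Report the proportion, Wald test and confidence interval among FAS subjects evaluable under that definition, meaning non-missing SABA and peak-flow baselines, alongside the all-FAS version.
2. Give the number evaluable for each diary criterion by arm.
3. Show the Definition 1 result in the same evaluable subset, so that the definitions are compared in the same people.
4. State that in the all-FAS version a subject with a null baseline is counted as without an event unless another criterion is met.

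Evaluability under Definitions 3 and 4 is fixed by pre-dose diary data, so the restriction does not condition on anything that happens after treatment starts.

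The cost is a few sentences, an evaluability flag and some extra table lines. The evaluable analysis will have fewer subjects, mostly post-Amendment 3 enrollees, and it drops non-diary events observed in excluded subjects. That is the reason to keep the all-FAS line beside it.
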